5.6.3 Vein Access Scale Assessment

At Visit 1 (day -7), study staff will complete the Vein Access Scale assessment to evaluate if the subject is a good candidate for the placement of the venous indwelling catheter. A score of seven to 10 is inclusive (Appendix 2).

5.6.4 Study Instructions/Query

Subjects will receive the following study instructions: fasting compliance (10-14 h, water only) and avoidance of alcohol 3 d prior to test visits (Visits 2, 3, and 4; days 0, 7, and 14]. Subjects will be queried about compliance with these instructions at Visits 2, 3, and 4 (days 0, 7, and 14).

5.6.5 24-h Record/Dispense Copy of 24-h Diet Record

Subjects will complete a 24-h Diet Record (Appendix 3) the day prior to Visit 2 (day 0). All foods and beverages consumed are to be recorded in the 24-h Diet Record. Subjects will be instructed to replicate the same diet intake the 24 h prior to Visits 3 and 4 (days 7 and 14). At the beginning of Visits 3 and 4 (days 7 and 14), a study staff member will review each subject's 24-h Diet Record completed prior to the visit and compare the food consumption to the first 24-h Diet Record (reviewed at Visit 2; day 0) for consistency. If the subject's food intake is not consistent with intake from the day prior to Visit 2, study staff should contact the Project Manager before continuing the visit. The test visit may be rescheduled at the discretion of the Biofortis Scientific Advisor or designee.

5.6.6 Pharmacokinetic Testing

A PK test will be initiated at Visit 2 (day 0). Subjects will be queried to confirm compliance with study instructions. If a subject fails to comply, the subject may be asked to reschedule the test day.

At Visit 2 (day 0), eligible subjects will arrive at the clinic fasted (10-14 h); after clinic visit procedures the PK test will begin with the insertion of an intravenous catheter at least 5 min prior to the first blood sampling time. In order to maintain patency of the intravenous catheter, the catheter will be flushed with 10 mL normal saline solution at least hourly. Should the catheter fail, blood samples will be drawn by venipuncture. Blood samples will be obtained at $t = -0.25 \text{ h} \pm 10 \text{ min}$ for the PK analysis of serum strontium followed by study product administration at t = 0 h. The study product will be dissolved with 100 mL of distilled water with an additional 100 mL of distilled water consumed immediately following. No food will be ingested for the subsequent 2-h period, but *ad libitum* water consumption will be allowed for remainder of visit following study product consumption. Water consumption will be recorded at the subsequent test visits. Blood samples will be obtained for the PK analysis of serum strontium at t = 1 and $2 \text{ h} \pm 5 \text{ min}$, where t = 0 h is the start of study product consumption. Subjects will be administered a standard breakfast immediately following the t = 2 h blood draw. Subjects will consume the breakfast meal in its entirety within 30 min.

Blood samples will be obtained via the indwelling venous catheter or venipuncture at $t=3,\,4,\,5,\,6$, and $8\,h\pm 5\,$ min, where $t=0\,h$ is the start of study product consumption, for the PK analysis of serum strontium. Subjects will be administered a standard lunch (immediately following the $t=6\,h$ blood draw), a standard snack (immediately following the $t=8\,h$ blood draw), and a standard dinner (at $t=10\,h$). Subjects will consume the meals/snack in their entirety within 30 min. The final blood draw will be obtained at $t=12\,h\pm 5\,$ min. The study product at Visits 3 and 4 (days 7 and 14) will be administered within \pm 30 min of the $t=0\,h$ time established at Visit 2 (day 0) and the meals/snack will be replicated.

Pharmacokinetic Test Day Schedule

Test time (t = "x" h)	Visits 2, 3, and 4 (days 0, 7, and 14)
t = -1.0 h	 Arrive at clinic; Study instructions query; Clinic visit procedures (vitals and body weight); Enrollment (Visit 2; day 0 only); AE assessment; IV inserted (at least 5 min prior to first blood draw)
t = -0.25 h ± 10 min	Blood sample obtained;Additional sample stored
t = 0 h	 Administer assigned study product; Ad libitum water consumption allowed for remainder of visit
$t = 1$ and $2 h \pm 5$ min	Blood sample obtained;Additional sample stored
Immediately following the t = 2 h blood draw	 Administer standard breakfast (consumed in 30 min);
$t = 3, 4, 5, and 6 h \pm 5$ min	Blood sample obtained;Additional sample stored
Immediately following the t = 6 h blood draw	Administer standard lunch (consumed in 30 min)
$t = 8 \text{ h} \pm 5 \text{ min}$	Blood sample obtained;Additional sample stored
Immediately following the t = 8 h blood draw	Administer standard snack (consumed in 30 min)
t = 10 h ± 5 min	Administer standard dinner (consumed in 30 min)
t = 12 h ± 5 min	 Blood sample obtained; Additional sample stored; AE assessment (immediately upon completion of blood sampling); Review study instructions; dispense copy and blank 24-h Diet Record (Visit 2 and 3 only)

5.7 Procedures at Each Clinic Visit

Procedures listed are not necessarily performed in the order below.

5.7.1 Screening (Visit 1; day -7)

- Informed consent/HIPAA
- Medical history
- Clinic visit
 - Height
 - Body weight
 - BMI assessment

- Vital signs
- Assess concomitant medication/supplement use
- Review inclusion/exclusion criteria
- Vein Access Scale
- Chemistry profile
- Hematology panel
- Capillary glucose
- In-clinic urine pregnancy test, where applicable
- Dispense 24-h Diet Record
- Review study instructions

5.7.2 Test Visits (Visits 2, 3, and 4; days 0, 7, and 14)

- Clinic visit
 - Body weight
 - Vital signs
 - Assess concomitant medication/supplement use
 - Review inclusion/exclusion criteria
- Study instruction query
- Collect/review 24-h Diet Record
- Assess AEs
- Capillary glucose
- Enrollment (Visit 2, day 0 only)
- PK Test
- Assess AEs
- Dispense copy (from day -1) of 24-h Diet Record (Visits 2 and 3; days 0 and 7 only)
- Dispense blank 24-h Diet Record (Visits 2 and 3; days 0 and 7 only)
- Review study instructions (Visits 2 and 3; days 0 and 7 only)

5.8 Early Termination Procedures

The term "Early Termination" refers to a subject's non-completion of the study. Should a subject decide to withdraw, all efforts will be made to complete and report observations as thoroughly as possible. In the event that a subject is withdrawn from the study, the reason for the withdrawal and the party who initiated the withdrawal (subject or Clinical Investigator) will be documented. Should the subject decide to withdraw, documentation of early termination and any AEs and concomitant medication use should be recorded.

The primary reason for a subject withdrawing prematurely should be selected from the following standard categories:

Adverse Event – event which results in discontinuation of the study product by the subject or that in the judgment of the Clinical Investigator for the best interest of the

subject requires discontinuation of study product (includes all categories of study product relatedness; Not Related, Unlikely, Possibly, Probably, and Definitely).

Death – death of the subject.

Withdrawal of Consent – subject desires to withdraw from further participation in the study in the absence of a medical need to withdraw determined by the Clinical Investigator.

Lost to Follow-Up – subject did not return for one or more follow-up visit(s) following dispensing of study product and could not be contacted thereafter. The reason for withdrawal was unknown and could not be documented.

Other – causes of premature termination from the study other than the above, such as theft or loss of study products, termination of study by Sponsor, etc.

6. Data Analysis and Statistical Methods

6.1 Outcome Variables

The outcome variables will include the following parameters for serum strontium at all three doses:

- Incremental area under the curve (iAUC) for serum strontium from pre-product consumption (t = -0.25 h) to 12 h (iAUC-_{0.25-12h})
- iAUC for serum strontium from pre-product consumption (t = -0.25 h) to infinity (AUC_{0- ∞})
- Maximum plasma concentration (Cmax)
- Time to Cmax (Tmax)
- Rate of elimination (λ_z)
- Half life $(t_{1/2})$
- Estimated fraction of the dose which is absorbed

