Stratum $Plus^{TM}$, is a highly pure form of strontium L-lactate (the strontium salt of L-lactic acid). Stratum Plus is manufactured in compliance with current Good Manufacturing Practices. The product has been thoroughly tested and meets rigorous purity specifications. It is free from contamination by D-lactic acid and trace metals known to harm human health. Unlike strontium renalate (and other related strontium salts), no clinical trials have been conducted with Stratum Plus. Thus, this study will be conducted to obtain pharmacokinetic (PK) information following acute oral intakes of three doses of Stratum Plus in healthy adults.

3. Objectives

The objective of this clinical trial is to obtain PK information following acute oral intakes of three doses of Stratum Plus in healthy adults.

4. Study Sample Population

Subjects will be healthy men and women 18-65 years of age, inclusive, with a body mass index (BMI) 18.0 to 31.9 kg/m². Subjects must also exhibit a body weight >60 kg, inclusionary.

5. Study Design and Procedures

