5.2 Study Design

This is an unblinded, crossover, sequential three dose study (Figure 1). The study will include one screening visit (Visit 1; day -7) and three test visits (Visits 2, 3, and 4; days 0, 7, and 14) with at least a 6-d washout between test visits.

[figure not shown]

Figure 1.

At Visit 1 (day -7), subjects will provide informed consent and undergo screening assessments including evaluations of medical history, prior/current medication/ supplement use, inclusion and exclusion criteria, height, body weight, BMI, vital signs, and Vein Access Scale (Appendix 2). A fasting capillary blood glucose will be assessed to establish each subject's fasting level and an in-clinic urine pregnancy test (all women <60 years of age) will also be obtained. Additionally, a fasting (10-14 h) blood sample will be collected for a chemistry profile and hematology panel. Study instructions will also be provided [fasting compliance (10-14 h, water only) and avoidance of alcohol 3 d

prior to test visits (Visits 2, 3, and 4; days 0, 7, and 14]. Subjects will then be dispensed a 24-h Diet Record (Appendix 3) with instructions to record intake the day prior to Visit 2 (day 0).

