At Visit 2 (day 0), subjects will arrive at the clinic fasted (10-14 h, water only, anchored to the t = -0.25 h blood draw) for the 12-h PK test visit. Subjects will undergo clinic visit procedures including: a review of inclusion/exclusion criteria, concomitant medication/supplement use, body weight, and vital signs assessment. Adverse events (AE) will be assessed and subjects will be queried about study instructions compliance. Additionally, the 24-h Diet Record will be collected and reviewed. A fasting capillary blood glucose will be assessed to confirm fasting status. Eligible subjects will be enrolled and will begin the PK test with the insertion of an intravenous catheter at least 5 min prior to the first blood sampling time. In order to maintain patency of the intravenous catheter, the catheter will be flushed with normal saline solution at least hourly. Blood samples will be drawn by venipuncture if the catheter fails. Blood samples will be obtained at $t = -0.25 \text{ h} \pm 10 \text{ min}$ for the PK analysis of serum strontium, where t = 0 h is the time of study product consumption. Additional blood samples will be collected at all timepoints for backup. Subjects will consume the study product in its entirety within 10 min at t = 0 h. The study product will be dissolved with 100 mL of distilled water with an additional 100 mL of distilled water consumed immediately following. No food will be ingested for the subsequent 2-h period, but ad libitum water consumption will be allowed for the remainder of the visit following study product consumption. Water consumption will be recorded at the subsequent test visits. Blood samples will be obtained for the PK analysis of serum strontium at t = 1 and $2 h \pm 5$ min, where t = 0 h is the start of study product consumption. Subjects will be administered a standard breakfast immediately following the t = 2 h blood draw. Subjects will consume the breakfast meal in its entirety within 30 min.

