5.5 Study Products

5.5.1 Description

- Low dose (170 mg Sr) strontium *L*-lactate
- Medium dose (340 mg Sr) strontium L -lactate
- High dose (680 mg Sr) strontium L -lactate

The study product will be provided as a dry powder packaged in individual vials. The study product will be prepared for consumption by dissolving the dry powder in the vial by adding 10 mL of distilled water and stirring the mixture. This liquid mixture will then be poured into an administration cup. An additional 10 mL of distilled water will be used to rinse the remaining study product into the administration cup. The remaining 80 mL of distilled water will be added directly into the administration cup. Following subject consumption of the 100 mL distilled water (with dissolved study product powder), another 100 mL will be added into the administration cup, swirled, and consumed by the subject. Study product information may be found in Appendix 5.

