5.6.2 Laboratory Measurements

The procedures for all clinical laboratory measurements will be outlined in a laboratory instruction sheet. **Lab**oratory parameters that are missing or have not been obtained must be entered in the eCRF as "not done."

The FDA-approved glucometer, with test strips from the same lot, will be used for determination of the in-clinic (Biofortis Clinical Research, Addison, IL) fasting capillary blood glucose (mmol/L) at Visits 1, 2, 3, and 4 (days -7, 0, 7, and 14) to ensure adequate fasting (10-14 h). Visits may be rescheduled for non-compliance, in the judgment of the Clinical Investigator.

The following will be performed as a part of the fasting (10-14 h) chemistry profile at Visit 1 (day -7): glucose, sodium, potassium, chloride, carbon dioxide, BUN, creatinine, calcium, osmolality, AST, ALT, ALP, total bilirubin, total protein, and albumin. Analytes will be assessed by Elmhurst Memorial Reference Laboratory (Elmhurst, IL).

The following will be performed as part of the fasting (10-14 h) hematology measurements at Visit 1 (day -14): WBC, RBC, hemoglobin concentration, hematocrit (as volume percent), MCV, MCH, MCHC, neutrophils, lymphocytes, monocytes, eosinophils, basophils and platelet count. Analytes will be assessed by Elmhurst Memorial Reference Laboratory (Elmhurst, IL).

Blood samples for the PK analysis of serum strontium will be collected at Visits 2, 3 and 4 (days 0, 7, and 14) at t = -0.25 h (\pm 10 min) and $t = 1, 2, 3, 4, 5, 6, 8, 10, and 12 h (<math>\pm$ 5 min), where t = 0 h is the start of study product consumption. Analytes will be assessed by NMS Labs (Willow Grove, PA). Additional samples will be stored as backup in the event the original sample is not viable.

An in-clinic urine pregnancy test will be performed on all women <60 years of age at Visit 1 (day -7).

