6.3 Statistical Analysis

All statistical analyses will be conducted using SAS for Windows (version 9.2, or higher, Cary, NC) and/or R 3.3.1 (R Core Team 2016). The data will be analyzed for the modified intent-to-treat population, which will include all subjects who complete all test visits. Subject data may also be excluded for the following reasons and possibly others:

• Non-compliance by the subject, including, but not limited to:

- o Missing appointments
- Use of prohibited drugs or any products thought to alter the outcome variables during the study
- o Not adhering to instructions as outlined in the protocol

All decisions regarding subject population and data inclusion will be documented prior to database lock.

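### Section 6.1 lists an absolute fraction of dose absorbed, which oral dosing with serum sampling cannot identify, and the plan states no outside clearance or volume to supply its level.

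*Combined protocol and SAP*

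**What the plan says.** Section 6.1 lists seven parameters for serum strontium at all three doses. The last is "Estimated fraction of the dose which is absorbed". No formula is attached. Section 6.5 plans descriptive statistics, including mean and SEM, for every continuous outcome at each dose. Nothing in Sections 6.1 to 6.7 says how this one is derived.

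The parts of the design that bear on it are:

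- **Route.** Oral only. Section 5.5.1 describes the vial contents being dissolved and drunk: "Following subject consumption of the 100 mL distilled water (with dissolved study product powder". The intravenous line mentioned in Section 5.2 ("insertion of an intravenous catheter at least 5 min prior to the first blood sampling time") is for drawing blood.
- **Specimen.** Section 5.6.2: "Blood samples for the PK analysis of serum strontium will be collected at Visits 2, 3 and 4". The only urine use is at screening: "An in-clinic urine pregnancy test will be performed on all women <60 years of age".
- **Prior data.** Section 2 says of this product that "no clinical trials have been conducted with Stratum Plus".
- **Design.** Section 5.2: "This is an unblinded, crossover, sequential three dose study". Every subject takes the low, medium and high dose in that order. There is no reference product.
- **Pre-lock decisions.** Section 6.3: "All decisions regarding subject population and data inclusion will be documented prior to database lock". This does not extend to pharmacokinetic constants.

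**The concern.** The outcome is worded as a fraction of the dose, which is an absolute quantity. To obtain it from serum after an oral dose, one needs clearance or volume from a separate source: an intravenous or tracer reference, excreted strontium, or a stated outside value. The design has none of the first two and the document states no value for the third.

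Two results are then possible. The analyst reports nothing for this outcome, or takes a clearance or volume from elsewhere and reports a percentage as a trial finding. In the second case the level of the percentage is an input, while the SEM beside it reflects only spread between subjects, so the figure looks much more certain than it is. The study is unblinded and the plan does not say when the constant would be fixed, so nothing rules out choosing it after strontium results have been seen. The stated objective is to obtain pharmacokinetic information on a product with no earlier trials, so a misread absorption figure touches the study's purpose.

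**Working it through.** The plan gives no figure for this outcome, so there is nothing to reproduce. The check is one of identifiability, followed by size. Doses of 170, 340 and 680 mg Sr, the completion goal of 6 and the enrolment target of 10 come from the document. All pharmacokinetic values and coefficients of variation (CVs) below are assumptions for illustration, including F = 0.25.

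**Step 1: what the data determine.** For a one-compartment oral model with k = CL/V:

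C(t) = F·D·ka / [V(ka − k)] × [exp(−k·t) − exp(−ka·t)], and AUC0-∞ = F·D/CL.

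F appears only as F/V and F/CL. Multiplying F, CL and V by one factor leaves every concentration unchanged. With ka = 0.7/h and half-lives of 4, 12 and 48 h, the sets (F, CL, V) = (0.125, 0.5x, 0.5x), (0.25, 1x, 1x) and (0.50, 2x, 2x) differ by exactly 0 at 1, 2, 3, 4, 5, 6, 8 and 12 h and on to 336 h. A second set of values (k = 0.015/h, ka = 0.8/h, CL/F = 3 L/h, F from 0.10 to 0.80) also gives a maximum difference of 0 at all three doses. This is an algebraic identity, and in any linear model F enters the same way. The 10 h sample, which Section 5.6.2 lists and the other schedules omit, makes no difference.

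**Step 2: Wagner-Nelson does not help.** With half-life 6 h and ka 0.7/h it returns 0.94 at 4 h and 1.00 at 12 h for true F of 0.125, 0.25 and 0.50 alike. It gives the share of the amount eventually absorbed, not of the dose.

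**Step 3: dependence on the outside constant.** F = CL × AUC0-∞ / Dose. Holding one illustrative AUC fixed at 340 mg, an assumed CL of 0.3, 0.6, 1.2 or 2.4 L/h gives F = 0.10, 0.20, 0.40 or 0.80.

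**Step 4: what the SEM would show.** SEM = 0.25 × CV / √n.

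| Between-subject CV | n = 6 | n = 10 |
|---|---|---|
| 20% | 0.020 | 0.016 |
| 30% | 0.031 | 0.024 |
| 40% | 0.041 | 0.032 |

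At n = 6, halving the constant moves the mean by 0.125, which is 0.125/0.041 to 0.125/0.020, or about 3 to 6 of the displayed SEMs. Doubling it moves the mean by 0.25, about 6 to 12 SEMs.

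**Step 5: what can be reported instead, and its limits.** Dose-normalised exposure needs no outside constant, but it equals relative absorption only if clearance and absorption timing are the same at each dose. Over assumed half-lives of 4 to 48 h, halving ka at one dose alone moves the AUC0-12h ratio to 0.92–0.87. Raising clearance by 20% at the same volume moves it to 0.88–0.985.

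CL/F needs AUC0-∞. At ka 0.7/h the share of AUC0-∞ lying beyond 12 h is 0.17, 0.30, 0.54, 0.74 and 0.86 for half-lives of 4, 6, 12, 24 and 48 h. It reaches 20% at a half-life of about 4.5 h and 30% at about 6.0 h.

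**The case against.** The best defence is that the word *Estimated* signals an intended outside clearance or volume, and that a value from another strontium salt might serve, since the assay measures strontium rather than lactate. The absence of trials with this product therefore does not show that no usable constant exists. That is right: the document supports *not stated*, not *unavailable*. But on this reading the reported level is still set by a number missing from the plan.

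Other points stand in part:

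- A single common clearance multiplies F equally at all doses, so a late choice cannot alter between-dose ratios or favour one dose. The harm is confined to the absolute level.
- Being unblinded adds little, since a constant could be chosen late under blinding too. The remedy is to fix it in advance.
- F = 0.25 and the two-fold range for clearance are illustrative. The SEM scales with the constant as well, so the asymmetry between 3–6 and 6–12 SEMs comes from using the original SEM as the yardstick. The proportionality does not depend on any of these choices.
- Extrapolation beyond 12 h is a separate matter. It matters here only if CL/F, or F computed from AUC0-∞, is reported.
- This is the last of seven unranked outcomes in a descriptive study with no hypothesis test. That limits the weight of the point but does not make the quantity estimable.

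**Conclusion.** The concern holds. The planned data identify CL/F and V/F but not F, at any sample size and any sampling duration, and the document supplies no constant to close the gap. The conclusion rests only on linear kinetics, oral-only dosing and serum-only assay, not on the assumed half-lives, ka or CVs. The error in level is proportional to the error in the assumed clearance: a factor of two either way turns 0.25 into 0.125 or 0.50. With assumed CVs of 20–40%, the SEM printed beside it would be only 0.020–0.041 at n = 6. Section 6.1 should be corrected. The other six outcomes do not depend on this constant, and no decision rule rests on the fraction.

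**What to change.** **Preferred.** In Section 6.1, replace the absolute fraction with dose-normalised, baseline-corrected AUC0-12h and Cmax, summarised as Section 6.5 already plans. Label them relative exposure, to be read as relative absorption only if clearance and absorption timing are constant across doses, and subject to the fixed dose order. Report CL/F only under a limit, stated in 6.1, on the extrapolated share of AUC0-∞ (for example 20%).

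**If an absolute fraction is kept.** State in 6.1, before any strontium results are available, the formula and the external clearance or volume with its source. Show F over a range of that constant, apply the same extrapolation limit if AUC0-∞ is used, and label the result assumption-based. The pre-lock documentation in Section 6.3 does not cover this.

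**Optional.** Within-subject dose ratios with confidence intervals. For paired contrasts the 90% factor is exp[t(0.95, n−1) × σw × √(2/n)], with σw = √ln(1 + CV²). At an assumed within-subject CV of 25% this is 1.33 at n = 6 and 1.22 at n = 10.

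**Cost.** Wording in 6.1 and simple arithmetic on data already collected, through a signed amendment submitted to the IRB under Section 9.1. No new visits or samples are needed. The sponsor gives up, or must qualify, an absolute absorption figure. A 20% limit would leave CL/F unreported unless the half-life is below about 4.5 h (30%: about 6.0 h) at the assumed ka of 0.7/h. Relative exposure is not proof of relative absorption.
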